4.4.2.3 Serious Adverse Events (including Adverse Events of Special Interest)

4.4.2.3.1 Last Vaccination

Last vaccination before an SAE (including AESIs) is the study vaccination at Visit 1 (D0).

4.4.2.3.2 Time of Onset

Time of onset will be computed using the same methodology than for unsolicited non-serious AEs described in Section 4.4.2.2.4.

SAEs (including AESIs) will be analyzed throughout the study using the following periods:

- Within 7 days after vaccination(s)
- Within 30 days after vaccination(s)
- During 6-month follow-up period: from D31 to the last telephone call on D180 (+ 14 days)
- During the entire study period: from D0 to the last telephone call on D180 (+ 14 days) (ie, all SAEs [including AESIs] occurred during the study)

An SAE (including AESI) with missing time of onset will be considered to have occurred just after the vaccination indicated by the visit number, so will be included in these tables.

Note: SAEs (including AESIs) that occurred before vaccination (negative time of onset) will not be included in analysis, but will be listed separately.

4.4.2.3.3 Duration

Duration will be computed using the same methodology as for unsolicited non-serious AEs described in Section 4.4.2.2.5.

4.4.2.4 Medically-Attended Adverse Events

MAAEs that occur within 30 days after vaccination(s) will be collected as unsolicited AEs. Unsolicited AEs that occur within the unsolicited period (within 30 days after vaccination[s]) or outside of the unsolicited period (from D31 to the 6-month follow-up telephone call on D180 [+ 14 days]) and have action taken of “Health care provider contact” will be summarized and presented as MAAEs. MAAEs will also be recorded in a MA from D30 after vaccination(s), until the 6-month follow-up telephone call on D180 (+ 14 days).

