4. The number and percentage of subjects reporting at least one of any MAAEs will be summarized throughout the trial.
5. The number and percentage of subjects reporting at least one of any SAEs will be summarized by study group, seriousness criterion, outcome, and by MedDRA preferred term and SOC, as well as by relationship to the study vaccine.
6. The number and percentage of subjects reporting at least one of any AESIs will be summarized throughout the trial.
7. Exact (Clopper-Pearson) 2-sided 95% CIs will be calculated for the percentages.

Additional subgroup safety analyses will also be provided by number of years (3 years, 4 years, 5 years, and 6 years) elapsed since priming vaccination received in either clinical studies MET50, MET43, or outside of Sanofi Pasteur trials, age group (13 to 17 years and 18 to 26 years), gender (Female and Male), and race (White, Asian, Black or African American, and Other).

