Unsolicited Adverse Event / Adverse Reaction:

An unsolicited AE is an observed AE that does not fulfill the conditions prelisted in the CRB in terms of diagnosis and / or onset window post-vaccination. For example, if headache between D0 and D07 is a solicited reaction (ie, prelisted in the protocol and CRB), then a headache starting on D07 is a solicited reaction, whereas, headache starting on D08 post-vaccination is an unsolicited AE. Unsolicited AEs includes both serious (SAEs) and non-serious unsolicited AEs.

Medically-Attended Adverse Event:

An MAAE is defined, for the purpose of this study, as a new onset of a condition that prompts the subject or subject's parent / guardian to seek unplanned medical advice at a health care provider's office or Emergency Department. This definition excludes pre-planned medical office visits for routine pediatric check-ups or follow-up visits of chronic conditions with an onset prior to entry in the study. Health care provider contact made over the telephone or by email will be considered a physician office visit for the purpose of MAAE collection. The outcome of the health care provider contact (whether it results in a prescription or not) will not be considered as a basis for reporting the event as an MAAE and all contacts should be reported. Sufficient data should be collected for the event to allow an assessment of the causality and diagnosis, if possible.

Injection Site Reaction:

An injection site reaction is an AR at and around the injection site. Injection site reactions are commonly inflammatory reactions. They are considered to be related to the product administered.

Systemic Adverse Event:

Systemic AEs are all AEs that are not injection or administration site reactions. Therefore, they include systemic manifestations such as headache, fever, as well as localized or topical manifestations that are not associated with the vaccination or administration site (eg, erythema that is localized but that is not occurring at the injection site).

Adverse Event of Special Interest:

An AESI is an event for which ongoing monitoring and rapid communication by the Investigator to the Sponsor must be done.

Such an event might warrant further investigation in order to characterize and understand it. Depending on the nature of the event, rapid communication by the study Sponsor to other parties (eg, regulators) might also be warranted.

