4.3.2.3.2 Reactogenicity (Solicited Reactions from Day 0 to Day 7 after Vaccinations)

After vaccination, subjects or the subjects' parent / guardian will be provided with a diary card, a digital thermometer, and a flexible ruler, and will be instructed how to use them. The following items will be recorded by the subjects or the subjects' parent / guardian in the diary card on the day of vaccination and for the next 7 days (ie, Day 0 through Day 7) until resolution:

- Daily temperature, with the route by which it was taken

- Daily measurement or intensity grade of all other solicited injection site and systemic reactions
- Action taken for each event (eg, medication)

The action(s) taken by the subjects or subjects' parent / guardian to treat and / or manage any **solicited reactions** will be classified in the CRB using the following list (all applicable items should be checked):

- None
- Medication
- Health care provider contact
- Hospitalized
- Discontinuation of study vaccination

Subjects or the subjects' parent / guardian will be contacted by telephone 8 days after vaccination to remind them to record all safety information in the diary card.

If the timing of the telephone call should fall on a weekend or a holiday, the call should be made on the next business day. If contact is not made on the designated day, study staff will continue calling until contact is made. Every telephone attempt and its outcome will be documented in the source document.

[Table 4.1](#) and [Table 4.2](#) present, respectively, the injection site reactions and systemic reactions that are prelisted in the diary cards and CRB, together with the intensity scales.

Table 4.1: Solicited injection site reactions: terminology, definitions, and intensity scales

CRB term (MedDRA lowest level term [LLT])	Injection site pain	Injection site erythema	Injection site swelling
Diary card term	Pain	Redness	Swelling
Definition	Pain either present spontaneously or when the injection site is touched or injected limb is mobilized	Presence of a redness including the approximate point of needle entry	Swelling at or near the injection site Swelling or edema is caused by a fluid infiltration in tissue or cavity and, depending on the space available for the fluid to disperse, swelling may be either soft (typically) or firm (less typical) to touch and thus can be best described by looking at the size of the swelling

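### The 30-day MAAE row counts unsolicited AEs only, so a solicited reaction that led to a health care contact meets the MAAE definition but is not counted

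*SAP*

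**What the plan says.** SAP 4.3.2.1 (and Protocol 9.3.2.1) says that an MAAE "is defined, for the purpose of this study, as a new onset of a condition" for which the subject or parent seeks unplanned medical advice. Planned check-ups and follow-up of chronic conditions that predate the study are excluded; solicited reactions are not. Whether the contact ends in a prescription "will not be considered as a basis for reporting the event as an MAAE and all contacts should be reported".

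The same section separates solicited from unsolicited events: "An unsolicited AE is an observed AE that does not fulfill the conditions prelisted in the CRB in terms of diagnosis" or onset window. Its headache example makes onset on D07 solicited and onset on D08 unsolicited.

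For solicited reactions, SAP 4.3.2.3.2 says that the actions taken "will be classified in the CRB using the following list (all applicable items should be checked"), and health care provider contact is on that list.

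SAP 4.4.2.4 then sets the MAAE derivation: "MAAEs that occur within 30 days after vaccination(s) will be collected as unsolicited AEs. Unsolicited AEs that occur within the unsolicited period", or after it up to the 6-month call, are the source. Those with a health care provider contact as action taken "will be summarized and presented as MAAEs". Table 5.2 marks the 30-day MAAE row as unsolicited. Protocol 9.3.2.2 (endpoint 6) and 9.3.2.5 state the same collection rule for MAAEs up to the D30 visit.

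Protocol 12.1.3 promises a wider summary: "The number and percentage of subjects reporting at least one of any MAAEs will be summarized throughout the trial".

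**The concern.** The definition and the derivation do not select the same events. Fever, headache or an injection-site reaction in the first week can prompt a visit, and the CRB has a box to record it. Such an event meets the MAAE definition, but the rule in SAP 4.4.2.4 looks only at unsolicited AEs.

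Two summaries are exposed: the 30-day MAAE row and the any-MAAE count over the whole trial. Any error runs in one direction. SAP 4.4.2.5.5 derives every solicited reaction as related, and Table 5.2 reports MAAEs by relationship. Every omitted event would therefore have been a related MAAE.

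**Working it through.** The plan states no MAAE rate, so there is no figure to reproduce. The check is a comparison of passages, followed by an illustration of size.

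**Step 1: follow one event through the rules.** Take a headache with onset on D03 that leads to an unplanned visit.
- MAAE definition (SAP 4.3.2.1): met.
- Solicited or unsolicited (SAP 4.3.2.1): solicited, because the term is prelisted and onset is by D07.
- Action taken (SAP 4.3.2.3.2): health care provider contact.
- MAAE derivation (SAP 4.4.2.4, Table 5.2): not selected, because the event is not an unsolicited AE.

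SAP 4.3.2.5 makes one explicit exception to the recording rule, for MAAEs that are also SAEs. It makes none for solicited reactions.

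**Step 2: which summaries change.**

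| Summary | Source | Affected? |
|---|---|---|
| MAAEs within 30 days | SAP 4.4.2.4.2, Table 5.2 | Yes |
| Any MAAE, whole trial | Protocol 12.1.3 | Yes |
| MAAEs D31 to D180 | SAP 4.4.2.4.2, Table 5.2 | No; solicited onset is D0 to D07 |
| Safety endpoint 6, D30 visit to 6 months | Protocol 9.3.2.2, SAP 4.3.2.2 | No; same reason |

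**Step 3: can a reader rebuild the count?** Table 5.2 lists action taken for solicited reactions, so the contacts are tabulated there. But a subject with contacts for fever, for headache and for a later unsolicited AE can appear in three places. Adding rows double-counts, and the plan specifies no subject-level count across solicited and unsolicited events.

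**Step 4: size, on assumptions.** Let s be the share of subjects with a solicited reaction leading to contact, and v the share of those already counted through an unsolicited MAAE. The understatement of the 30-day percentage is s × (1 − v). The documents give neither s nor v.

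| Assumed s | Subjects of 600 | Understatement, v = 0 | Understatement, v = 0.5 |
|---|---|---|---|
| 0% | 0 | 0 | 0 |
| 0.5% | 600 × 0.005 = 3 | 0.5 points | 0.25 points |
| 1% | 600 × 0.01 = 6 | 1.0 points | 0.5 points |
| 2% | 600 × 0.02 = 12 | 2.0 points | 1.0 points |

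For scale, suppose the row as planned showed 5% of 600 (also assumed). With exact 95% intervals and v = 0, 30/600 = 5.0% (3.4 to 7.1) becomes:
- s = 0.5%: 33/600 = 5.5% (3.8 to 7.6)
- s = 1%: 36/600 = 6.0% (4.2 to 8.2)
- s = 2%: 42/600 = 7.0% (5.1 to 9.3)

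In a group of 200, s = 2% moves 10/200 = 5.0% (2.4 to 9.0) to 14/200 = 7.0% (3.9 to 11.5).

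**The case against.** A reader might infer more than the documents support, and the case against those stronger readings is good.

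- *The MAAE endpoint is understated.* It is not. Endpoint 6 runs from the D30 visit to the 6-month contact, and no solicited reaction can start in that window.
- *The SAP introduced an error.* It did not. It carries out the collection rule in Protocol 9.3.2.2 and 9.3.2.5. The tension is between the protocol's MAAE definition and that rule.
- *A difference between Group 1 and Groups 3 and 4 would be hidden.* Groups 3 and 4 receive two injections on D0, so more care-seeking for reactions is conceivable, but the documents give no rate. Protocol 12.1.3 summarizes action taken for solicited reactions by study group, so a contrast would show there. Even assumed shares of 1% and 3% give 2/200 (0.1 to 3.6%) and 6/200 (1.1 to 6.4%), Fisher p = 0.28.
- *The events are certain never to be counted.* Protocol 9.3.2.5 has D0 to D30 MAAEs recorded as unsolicited, with no stated exception for prelisted terms. Site instructions, which are not among the documents, might route some events that way. The definitions in SAP 4.3.2.1 point the other way.

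It is also fair that safety is descriptive with no hypothesis tested, and that solicited reactions are not listed as carrying the seriousness and outcome descriptors that the MAAE row calls for. A full merger would leave those cells blank.

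What remains is narrow: under the stated rule, events that meet the definition are outside two planned summaries, and the subject-level count cannot be rebuilt from the separate tables.

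**Conclusion.** The point holds for the 30-day MAAE row and the whole-trial MAAE count, and for nothing else. The direction is known (downward, and only for related events); the size is not. It is zero if no subject's only medically attended event was a solicited reaction. It is about 0.25 to 2.0 points if s is 0.5 to 2% and v is 0 to 50%, and those ranges are assumptions. The primary objectives, error rate, power and sample size are untouched. No data are lost. This is a low-cost improvement to a descriptive safety table.

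**What to change.** In SAP 4.4.2.4 and Table 5.2:

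1. Label the existing 30-day MAAE row as covering unsolicited AEs only.
2. Add, by group, the number and percentage of subjects with at least one AE of any kind, solicited or unsolicited, within 30 days with health care provider contact as action taken. Show solicited and unsolicited sub-rows.
3. Use the same any-AE count for the whole-trial summary promised in Protocol 12.1.3. SAP 4.4.2.4.2 lists only the two separate periods, so this row needs to be named.

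The action-taken field is already collected for both kinds of event, so the cost is a short SAP edit and minor programming. There are three drawbacks. The MAAE rate may look slightly less favourable. The same event will appear in both the solicited and the MAAE tables, which a footnote should say. The solicited component will have no seriousness or outcome descriptors, so the addition should stay a count row and not be merged into the full MAAE description.

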4.4.2.4.1 Last Vaccination

Last vaccination will be derived using the same methodology as used for unsolicited non-serious AEs described in Section [4.4.2.2.3](#).

4.4.2.4.2 Time of Onset

Time of onset will be computed using the same methodology as used for unsolicited non-serious AEs described in Section [4.4.2.2.4](#).

MAAEs will be analyzed throughout the study using the following periods:

- Within 30 days after vaccination(s)
- During 6-month follow-up period: from D31 to the last telephone call on D180 (+ 14 days)

An MAAE with missing time of onset will be considered to have occurred just after the vaccination indicated by the visit number, so will be included in the safety analysis tables mentioned above.

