4.4.2.2.3 Last Vaccination

Last vaccination before any unsolicited non-serious AE is the study vaccination at Visit 1 (D0).

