4.4.2.2.4 Time of Onset

Time of onset is derived from the start date of the unsolicited non-serious AE provided in the clinical database and the date of last vaccination:

Start date of the unsolicited non-serious AEs – date of last vaccination

The time of onset should be considered as missing only if one or both of the dates are missing or partially missing.

The unsolicited non-serious AEs will be analyzed “Within 30 days”, which corresponds to AEs with a time of onset between D0 and D30 after vaccination(s) or missing. An AE with missing time of onset will be considered to have occurred just within 30 days after the vaccination indicated by the visit number, so will be included in the safety analysis.

Note: Unsolicited non-serious AEs that occurred before vaccination (negative time of onset) or with onset higher than defined above (eg, > 30 days after vaccination[s]) will not be included in the safety analysis, but will be listed separately.

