5.3.1.5 Start Date and Stop Date

Missing or partially missing start dates for unsolicited AEs will remain missing and not be imputed. If the start date is missing or partially missing, the time of onset will be considered to be missing. Nevertheless, unsolicited AEs with missing time of onset will be included in analyses according to the visit collected.

Missing or partially missing stop dates for AEs (solicited reactions and unsolicited AEs) will remain missing and not be imputed.

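### SAP 4.4.2.3.2 and 4.4.2.4.2, read literally, place incompletely dated SAEs and MAAEs at D0, while SAP 5.3.1.5 assigns them by visit collected; no precedence is stated

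*SAP*

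**What the plan says.** SAP 4.4.2.2.4 defines when onset is missing: "The time of onset should be considered as missing only if one or both of the dates are missing or partially missing". Sections 4.4.2.3.2 (SAEs, including AESIs) and 4.4.2.4.2 (MAAEs) adopt that method.

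For MAAEs, 4.4.2.4.2 then states: "An MAAE with missing time of onset will be considered to have occurred just after the vaccination indicated by the visit number". For SAEs, 4.4.2.3.2 states: "An SAE (including AESI) with missing time of onset will be considered to have occurred just after the vaccination indicated by the visit number".

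The vaccination meant is fixed elsewhere. Sections 4.4.2.2.3 and 4.4.2.3.1 name the Visit 1 (D0) vaccination as the last vaccination before any non-serious unsolicited AE or SAE, and 4.4.2.4.1 carries this over to MAAEs.

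The reporting periods differ by event type. SAEs are tabulated within 7 days, within 30 days, from D31 to the 6-month call, and over the entire study. MAAEs have two periods only: within 30 days, and D31 to the 6-month call.

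SAP 5.3.1.5 covers the same situation differently. Missing or partly missing start dates are not imputed, and "unsolicited AEs with missing time of onset will be included in analyses according to the visit collected".

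**The concern.** Assigning undated events to the vaccination suits a 30-day diary, where nearly every onset falls inside the window. It suits SAEs and MAAEs less well, because these are also gathered by memory aid and a telephone call at D180 (+14 days). Telephone Call 2 involves no study vaccination and is not a numbered visit in SAP Tables 3.1 and 3.2. For an event first reported there, the visit-number phrase in 4.4.2.3.2 and 4.4.2.4.2 has no clear meaning other than D0.

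On that reading, misplacement runs one way, from late follow-up into the period just after the booster. Early SAE, AESI and MAAE rates would be overstated and follow-up rates understated. Two programmers could also produce different tables from the same data, one following the event-specific sections and the other following 5.3.1.5.

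**Working it through.** No stated figure depends on this point, so there is none to reproduce. The check sets the rules side by side and then sizes a single misplaced event.

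**1. Do both rules cover the same events?** Yes. SAP 4.3.2.1 includes SAEs among unsolicited AEs, and 4.4.2.4 derives MAAEs from unsolicited AEs with a health care provider contact. The rule in 5.3.1.5 therefore reaches both types that 4.4.2.3.2 and 4.4.2.4.2 cover.

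**2. What does each rule do with m undated events first collected at Telephone Call 2?**

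| Row | 4.4.2.3.2 / 4.4.2.4.2, literal | 5.3.1.5, visit collected |
|---|---|---|
| SAE, within 7 days | m | 0 |
| SAE, within 30 days | m | 0 |
| SAE, D31 onward | 0 | m |
| SAE, entire study | m | m |
| MAAE, within 30 days | m | 0 |
| MAAE, D31 onward | 0 | m |

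The second column takes Telephone Call 2 as the collecting visit. That is the natural reading, but 5.3.1.5 does not spell it out.

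**3. Does a known month help?** Not under the literal rule. Illustration: D0 is 10 January 2020, and at the 6-month call the subject reports an event in May with the day unknown. The earliest possible onset is 1 May. Days from 10 January: 21 (rest of January) + 29 + 31 + 30 + 1 = 112, so onset is D112 or later. The date is still partly missing, so onset is missing and the event is placed just after D0.

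**4. Share of follow-up in each period.** Counting D0 to D180 as 181 days: D0–D7 is 8/181 = 4.4%, D0–D30 is 31/181 = 17.1%, and D31–D180 is 150/181 = 82.9%. If follow-up runs to D194 (195 days), the shares are 8/195 = 4.1%, 31/195 = 15.9% and 164/195 = 84.1%. On the assumption of uniform onset, about 83–84% of undated events would belong to D31 onward. The documents give no onset distribution.

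**5. Effect of one misplaced subject.** Inputs are the planned group sizes (200 in Groups 1 and 2, 100 in Groups 3 and 4) and the Clopper-Pearson 95% interval that the SAP uses for safety percentages. With 0 events the upper limit is 1 − 0.025^(1/n). With 1 event the lower limit is 1 − 0.975^(1/n), and the upper limit is the 0.975 quantile of Beta(2, n − 1).

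| n | 0 events | 1 event |
|---|---|---|
| 200 | 0% (0 to 1.8%) | 0.5% (0.01 to 2.8%) |
| 100 | 0% (0 to 3.6%) | 1.0% (0.03 to 5.4%) |

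**The case against.** The strongest answer is that 5.3.1.5 already keeps these events in the right period. A reader might infer from 4.4.2.3.2 and 4.4.2.4.2 alone that late events will be counted as early. The documents do not settle that: 5.3.1.5 points the other way, and no precedence is given. This part of the objection stands, so the supportable finding is a conflict in which one branch gives a wrong period, not an established misclassification.

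A reader might also infer that the SAE endpoint is distorted. It is not. SAP 4.3.2.2 (item 5) defines that endpoint from D0 to the end of the trial, and the entire-study row is the same under either rule. The 7-day row exists for SAEs only. Only the MAAE endpoint (item 6) names a later window.

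Third, undated events should be uncommon. The memory aid is kept from D30 and reviewed at the call (Protocol 5.1.3 and 5.1.4), and start dates are required for every unsolicited AE (Protocol 9.3.2.3.3). Missing information must be explained (Protocol 11.1), and queries closed before lock (Protocol 13.4.1). SAEs are reported within 24 hours and reconciled with the pharmacovigilance database (Protocol 10.1 and 11.2). This also stands, especially for SAEs. It lowers the expected number but does not tell the programmer which rule to apply.

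Finally, safety is descriptive, listings must show incomplete dates (SAP 5.3.1), and leaning early can be called conservative. That limits the consequence. But placing an event in a window that its known month excludes is an error, and conservatism is better served by a labelled worst-case count.

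**Conclusion.** The concern holds as an unreconciled conflict. Read literally, two event-specific sections send any SAE or MAAE with an incomplete start date to D0, even where the known month rules out onset within 30 days. The general missing-data section sends it to the visit collected. The SAP does not say which governs, or what visit number means for an event first reported at Telephone Call 2.

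The effect is limited to period assignment in descriptive tables. The primary objectives and the entire-study SAE count are untouched. Per misplaced subject, a row changes by 0.5 percentage points in a group of 200 or 1.0 in a group of 100. A reader might want to convert this into an overall inflation of the 30-day MAAE rate. That would need the late MAAE rate, the share with incomplete dates and the true 30-day rate, and the documents give none of them. The 83–84% share rests on uniform onset and shows only where most undated events would be expected to fall.

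**What to change.** State one rule in SAP 4.4.2.3.2 and 4.4.2.4.2, consistent with 5.3.1.5, and align 4.4.2.2.4, which uses the same visit-number wording for non-serious unsolicited AEs.

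1. Use the known date parts first. If the earliest possible onset is after D30, assign the event to D31–D180 (+14). Count an SAE in the 7-day row only if its known date parts are compatible with D0–D7. This bounds the period without imputing a date, so it does not breach 5.3.1.5.
2. If the date is fully missing or still ambiguous, assign by the contact at which the event was first reported: D30 visit to within 30 days, Telephone Call 2 to D31 onward. Name the contacts, because 5.3.1.5 speaks only of visits.
3. Footnote every event assigned this way and give a worst-case-early count.

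The cost is a few sentences and a small programming change before database lock, with no new data. There are two small downsides. An undated early event first reported at the 6-month call is placed late. An undated D31–D44 event reported at a late D30 visit is placed early, since Protocol 5.2.7.1 lets that visit's blood draw run to day 44. The footnote discloses both.
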